### 5.3. Measurements of study drug compliance

Study drug in this study refers to the injection of the contrast media. Number of subjects with theoretical volume to be administered not equal to the one actually administered will be presented and the difference for those subjects will be tabulated in mL and percentage:

$$Compliance = \left(1 - \frac{theoretical\ volume - actual\ volume}{theoretical\ volume}\right) \times 100$$

### 5.4. Demographic and other baseline characteristics

#### 5.4.1. Demographic data

Demographic parameters are age, sex, childbearing potential, body weight in kilograms (kg), height in centimetres (cm), BMI (kg/m^2) and ethnic origin (self-reported race/ethnicity). Summary statistics (number [n], mean, standard deviation [SD], median, minimum, and maximum) will be calculated for age, body weight, height and BMI. Frequency and percentages will be calculated for sex.

BMI will be derived for each collection of body weight using the formula:

$$BMI = \frac{Body\ Weight\ (kg)}{Height\ (m)^2}$$

#### 5.4.2. Study disease

Not Applicable.

#### 5.4.3. Risk factors

Not Applicable.

#### 5.4.4. Medical history and concomitant diseases

Medical history and concomitant diseases will be coded in System Organ Classes (SOC) and preferred terms (PT) using the Medical Dictionary for Regulatory Activities (MedDRA) version 21.0 or the latest version available at the date of data base lock. Medical histories are the ones flagged as "Not Ongoing" and concomitant diseases are those flagged as "Ongoing" at the screening visit.

Summary tables (number and % of subjects) grouped by SOC and PT will be presented by sequence group and overall for Medical history firstly then for concomitant diseases.

Listing of demographics, study disease characteristics and all diseases will be presented in CSR Appendix 16.2.4 with a flag for ongoing diseases.

CONFIDENTIAL	STATISTICAL ANALYSIS PLAN N° GDX-44-006 VERSION N° 2.0      DATED: 24JUL2018	██████████ Page 25 / 57
--------------	---	----------------------------

#### **5.4.5. Clinical laboratory evaluation at baseline**

Laboratory data analysis will be done using the safety set by sequence group and overall. Blood samples will be performed during screening visit. Urinalysis data will be listed only.

Results will be presented in standard international (SI) units and conventional United States units (See Table 1 and Table 2 respectively). Original units will only be listed. Laboratory data will be analyzed quantitatively and qualitatively. Qualitative analyses will be done via comparison of laboratory data to their reference ranges. Quantitative analyses will be done by tabulating raw data.

#### **5.4.6. Vital signs, physical findings and other observations related to safety at baseline**

Abnormality detected during physical examination will be listed in section 16.2.9., it will be described in the Adverse Events section.

Summary statistics (number [n], mean, standard deviation [SD], median, minimum, and maximum) will be calculated for vital signs (systolic blood pressure, diastolic blood pressure and pulse rate) at screening visit and presented by sequence group and overall. Qualitative analyses of Systolic/Diastolic Blood Pressure (mmHg) and Pulse Rate (beats/min) will be done via comparison of vital signs data to their normal ranges.

#### **5.4.7. Prior medication and procedures**

Prior therapies are defined as therapies ended before the first administration.

Prior medications will be coded using the WHODRUG dictionary version September 2016. Prior procedures are therapies not coded as per WHODRUG dictionary.

The number and percent of subjects taking prior medications and procedures will be presented by sequence group and overall.

Summary tables (number and % of subjects) grouped by the first and the fourth level of ATC code will be presented by sequence group and overall for prior medication.

Listing of all prior therapies will be presented in CSR appendix 16.2.4.

#### **5.4.8. 12-lead ECG assessment**

Summary statistics (number [n], mean, standard deviation [SD], median, minimum, and maximum) will be calculated for cardiac status from the mean of the ECG triplicate examination at screening visit by sequence group and overall (QT, QTcF, QTcB, QRS, PR, RR, heart rate). Frequency and percentages will be calculated for sinus rhythm (yes/no). The number (%) of subjects having at least one “No” for sinus rhythm or having all “Yes” will be summarized.

#### **5.4.9. Other baseline characteristics**

Data concerning contrast agent history at screening and inclusion and pregnancy test will be only listed in section 16.2.4.

Meal date and start and end time will be listed for each period.

CONFIDENTIAL	
STATISTICAL ANALYSIS PLAN N° GDX-44-006
 
VERSION N° 2.0      DATED: 24JUL2018
	
██████████
 
Page 26 / 57

--------------	--	---

## 5.5. Cardiac safety evaluation

All cardiac safety analysis will be conducted using the FAS except otherwise specified. Listing of all cardiac safety data will be presented in CSR appendix 16.2.6. Listing of drug concentration data will be presented in CSR appendix 16.2.5.

### 5.5.1. Primary analysis of the primary criteria

Cardiac safety data are coming from 12-lead Holter ECG recording read by off-site cardiologists. Triplicate values will be issued for each measurement and the average of the 3 replicates will be used for statistics analyses. Therefore there will be one measure by timepoint by subject.

#### 5.5.1.1 Baseline value

There will be one baseline by administration period.

The baseline is defined as the mean of the 3 triplicates ECGs measured within one hour before each IMP/AMP administration (i.e., first the mean of the 3 triplicates ECGs is done for each timepoint prior IMP/AMP administration: 45, 30 and 15 minutes before administration, then the 3 means are averaged).

#### 5.5.1.2 Primary analysis

The primary analysis is performed using an analysis of covariance (ANCOVA) model for crossover data with baseline data as covariate, sequence, period, trial drug and sex as fixed effect and subject as a random effect.

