11.3.6 Cardiac safety Data

Cardiac safety data are coming from 12-lead Holter ECG recording read by off-site cardiologists. Triplicate values will be issued for each measurement and the average of the 3 replicates will be used for statistics analyses. Therefore there will be one measure by timepoint by subject.

- **Baseline value**

There will be one baseline by administration period.

The baseline is defined as the mean of 3 triplicates ECGs timepoint measurements within one hour before each IMP/AMP administration.

- **Primary analysis**

Primary analysis will be done using the Per Protocol Set

Primary endpoint is defined as the largest time-matched placebo-corrected, change-from-baseline mean effect of the two P03277 doses of QT interval expressed as QTc according to Fridericia's formula ($\Delta\Delta\text{QTcF}$) (in ms).

The primary analysis is performed using an analysis of covariance (ANCOVA) model for crossover data with baseline data as covariate, sequence, period, time, trial drug, trial drug by time and sex as fixed effect and subject as a random effect.

Test

Differences between means will be tested through the model for each timepoint and for the two doses of P03277 using Student's t-test according to the following items:

- μ_{ij} is the expected average of QTcF for each dose of P03277 at each timepoint (where i is corresponding to one timepoint and j to the 2 doses)
- μ_{ij0} is the expected average of QTcF for corresponding placebo

Null hypothesis

$H_i: \mu_{ij} - \mu_{ij0} \geq 10, i = 1 \dots 9, j=1,2$

Alternative hypothesis

$K_i: \mu_i - \mu_{i0} < 10, i = 1 \dots 9, j=1,2$

For each timepoint, the two-sided 90% confidence intervals of the difference between each of the two doses of P03277 and placebo is calculated for testing above hypotheses.

The trial will be considered as successful if, no test is significant that is to say if the upper range of the 90% CI is lower than 10 ms for all tests.

The appropriateness of a linear model will be assured by inspecting the goodness of fit, e.g., by looking at normal QQ-plots for the residuals and plots of the residuals over predicted values. If there is an indication that a linear model is inappropriate, the nonlinearity detected will be taken into account by an appropriate transformation of the concentration values (e.g., $\log(\text{conc}/\text{lloq})$) or by the use of an appropriate nonlinear model.

- **Secondary analysis:**

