### 3.4. Adjustment for covariates

For the primary analysis and the assay sensitivity, QTcF at baseline and sex are considered as covariates taken into account in the models used for the analyses.

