## **4. CHANGES IN THE CONDUCT OF THE STUDY OR PLANNED ANALYSES**

Primary analysis will test each timepoint: 11 instead of 9 mentioned in the protocol.

A model will be performed for each timepoint, the time will no more be included in the model. There is no change on the statistical analysis as Intersection-Union test was planned.

In secondary analysis, same analysis as for primary endpoint will be repeated for HR in addition of QT, QTcPOP and QTcB.

Descriptive analysis on number and percentage of subjects showing values above predefined threshold will be presented for PR and QRS.

CONFIDENTIAL	
STATISTICAL ANALYSIS PLAN N° GDX-44-006
 
VERSION N° 2.0      DATED: 24JUL2018
 
██████████
	
██████████
 
Page 16 / 57

--------------	--	---

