#### SAS procedure:

```
proc mixed data = dataset method = REML plots=all;
  class Seq Per Trt subj gender;
  model  $\Delta QTcF = \text{Baseline } Seq Per Trt gender /$  ddfm = kr residual outp=ipred outpm=pred;
  random subj / type = cs;
```

CONFIDENTIAL	STATISTICAL ANALYSIS PLAN N° GDX-44-006  VERSION N° 2.0      DATED: 24JUL2018  ██████████	██████████  Page 27 / 57
--------------	---	--------------------------------

```
lsmeans Trt;
Estimate "P03277 0.1 mmol/kg - Placebo 5min after administration" Trt 1 0 0 -1 / alpha = 0.1
cl;
run;
```

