#### Assay sensitivity analysis

The assay sensitivity analysis is performed using an analysis of covariance (ANCOVA) model for crossover data with baseline data as covariate, sequence, period, trial drug and sex as fixed effect and subject as a random effect.

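### The crossover ANCOVA gives the period baseline a single slope with subject random, so the drug-placebo contrasts are under-adjusted and lose some precision; validity and the stated N = 40 are not affected.

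*SAP*

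**What the plan says.** SAP 5.5.1.1 states: "There will be one baseline by administration period". Each baseline averages readings taken "45, 30 and 15 minutes before administration, then the 3 means are averaged", so a subject who completes the trial has four.

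SAP 5.5.1.2 analyses change in QTcF as follows: "analysis of covariance (ANCOVA) model for crossover data with baseline data as covariate, sequence, period, trial drug and sex as fixed effect and subject as" (subject is random). The SAS code that follows has one term for baseline and the statement "random subj / type = cs". SAP section 4 adds: "A model will be performed for each timepoint, the time will no more be included in the model", so there is one such slope at each timepoint. SAP 3.4 names the covariates: "QTcF at baseline and sex are considered as covariates taken into account in the models used for the analyses".

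SAP 5.5.2 uses the same form for moxifloxacin: "The assay sensitivity analysis is performed using an analysis of covariance (ANCOVA) model for crossover data with baseline data as covariate, sequence, period". Protocol 11.3.6 also has a single baseline term: "model for crossover data with baseline data as covariate, sequence, period, time, trial drug, trial drug by time and sex as fixed effect". SAP 5.5.4.1 repeats the primary analysis for QT, QTcPOP, QTcB and HR.

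Neither document separates a subject's mean baseline from the period-to-period deviation, or fits subject as fixed.

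**The concern.** In a crossover, the comparison of drug with placebo is made within subjects. A baseline that happens to read high in one period lowers the change score of that period. The slope that removes this noise is the within-subject slope, for this period's baseline against the same subject's other baselines.

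The between-subject slope answers a different question: do subjects with long QTcF change more or less than subjects with short QTcF? A subject's own level cancels from a change score, so that slope is close to 0. With subject random and one coefficient, the fitted slope is a compromise. It is pulled towards 0 when baselines spread more between subjects than within them, and baseline noise then stays in the contrasts.

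The stake is precision. Success needs all 22 upper limits (11 timepoints, two doses) below 10 ms, and a negative study also needs assay sensitivity. Both use this model.

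**Working it through.** **Inputs from the documents.** Within-subject SD 9 ms, expected difference 2 ms, margin 10 ms, one-sided 5%, power 85%, N = 40, L = 9 (protocol 11.2, SAP 3.3); 11 timepoints (SAP section 4); baseline averaged over three pre-dose times (SAP 5.5.1.1).

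**Assumed, because the documents give no values.** Between-subject SD s = 10 to 20 ms; day-to-day SD d = 0 to 8 ms; errors of the three baseline readings independent or correlated 0.4.

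**Step 1: the plan's own figure.** N = 2(t_α + t_β′)²[σ/(δ − 10)]², with N − 2 degrees of freedom and β′ = 1 − 0.85^(1/L).
- L = 9: β′ = 0.0179 and N = 38, within 2 of the stated 40.
- L = 11: β′ = 0.0147 and N = 40.

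The stated 40 stands.

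**Step 2: the two slopes.** Write baseline = subject + day + error (variance v_b), and post-dose = subject + day + error (variance v_p). The change is then the difference of the two errors, so v_p + v_b = 9² = 81. With independent readings v_b = v_p/3, which gives v_p = 60.75 and v_b = 20.25.
- Within-subject slope = −v_b/(d² + v_b). For d = 0, 3, 5 and 8 ms: −1.00, −20.25/29.25 = −0.69, −20.25/45.25 = −0.45, −20.25/84.25 = −0.24.
- Between-subject slope over four periods = −(v_b/4)/(s² + (d² + v_b)/4). At s = 15, d = 3: −5.06/232.3 = −0.02.
- Within-subject variance left at slope b: V(b) = 81 + 2b·v_b + b²(d² + v_b).

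In large samples the single slope minimises 3·log V(b) + log(b²s² + V(b)/4). At s = 15, d = 3 that gives b = −0.084, and V = 81 − 3.40 + 0.21 = 77.8. At the within-subject slope, V = 81 − 20.25²/29.25 = 67.0. The ratio is 67.0/77.8 = 0.86.

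**Step 3: finite samples.** REML simulation of the 4×4 Williams design, N = 40, SD of change 9 ms, planned model against split baseline. Over 24 settings the single slope was −0.05 to about −0.35, against a within-subject slope of −0.23 to −1.0. The variance ratio (split over planned) was 0.68 to 0.99. At s = 15 ms the variance fell by about:

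| Day-to-day SD | Readings independent | Readings correlated 0.4 |
|---|---|---|
| 0 ms | 20% | 28% |
| 3 ms | 13% | 20% |
| 5 ms | 7% | 12% |
| 8 ms | 2% | 5% |

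**Step 4: in milliseconds and power.** At N = 40, SE = 9·√(2/40) = 2.01 ms and the 90% half-width is 1.686 × 2.01 = 3.39 ms. A variance ratio r multiplies both by √r. Power in the plan's formula is [1 − P(T₃₈ > 8/(2.01√r) − 1.686)]^11.

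| r | Half-width (ms) | Shorter by (ms) | Power, L = 11 |
|---|---|---|---|
| 1 | 3.39 | – | 86% |
| 0.98 | 3.36 | 0.03 | 87% |
| 0.93 | 3.27 | 0.12 | 90% |
| 0.87 | 3.16 | 0.23 | 93% |
| 0.80 | 3.03 | 0.36 | 95% |

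With L = 9 the starting power is 88%. This step takes 9 ms as the SD that applies under the planned model.

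**The case against.** The strongest reply is that nothing here is an error. The planned model is coherent and pre-specified, its contrasts are unbiased by randomization, and wider limits are conservative against the 10 ms margin. If 9 ms already describes the residual of the planned model, the sample size already carries the cost. All of this stands.

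The size is also open. It depends on variances that appear nowhere in the documents, and the largest savings need a true QTcF level that is the same on all four dosing days. With independent readings the within-subject slope cannot save more than 20.25/81 = 25% of the variance of the raw change. In absolute terms the gain is tenths of a millisecond or less over most of the range. At a true difference of 2 ms the expected upper limit is already about 2 + 3.39 = 5.4 ms.

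Three stronger readings are tempting, and the documents do not support them:
- That the slope is always set mainly by differences between subjects. In a second set of 48 assumed settings, which varied the within-subject correlation between baseline and post-dose values from 0.2 to 0.8, it lay nearer the between-subject value in 40, not in all. The excess variance was only 0.5% to 5% at a correlation of 0.8.
- That the trial is badly underpowered because 22 independent tests must all succeed. The two doses share the placebo data, and timepoints within a period share a baseline, so the tests are correlated. The number of tests is in any case a separate matter from the baseline slope.
- That the same gain applies to QT, QTcPOP, QTcB and HR. The calculation fixes only the 9 ms for QTcF.

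What the reply does not remove is the direction: in all 24 simulated settings the split model had the lower contrast variance.

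**Conclusion.** The point holds as a loss of precision. One slope with subject random under-adjusts the within-subject contrasts when baselines vary more between than within subjects. The variance that could be saved is about 1% to 32% over the assumed ranges, and only a few percent or less if day-to-day variation is near 8 ms. A reader should not infer bias, invalid intervals or a wrong N: none of these follows. The case for changing the model rests on its low cost and on using baselines that are collected anyway, not on a demonstrated shortfall in power.

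**What to change.** Before unblinding, in SAP 5.5.1.2 and 5.5.2 and their SAS code, replace the single baseline covariate by two:
1. the subject's mean of the available period baselines;
2. the period baseline minus that mean.

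Keep sequence, period, trial drug, sex and random subject as they are. Define which baselines count as available, since the moxifloxacin period has no ECG reading at 5, 10 and 20 minutes and some subjects may drop out.

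Record the change in SAP section 4 as a departure from protocol 11.3.6; that section already records the removal of time from the model. Use the same two covariates in the repeated QT, QTcPOP, QTcB and HR analyses for consistency, without claiming a size of gain there.

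The cost is SAP wording, two derived variables and one degree of freedom. No new data are needed. A change made after unblinding would look data-driven.

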#### Test

Differences between means will be tested through the model for each timepoint and for the two doses of P03277 using Student's t-test.

For each timepoint, the two-sided 90% confidence intervals of the difference between each of the two doses of P03277 and placebo is calculated for testing the hypotheses.

The trial will be considered as successful if no test is significant that is to say if the upper range of the 90% CI is lower than 10 ms for all tests.

The appropriateness of a linear model will be assured by inspecting the goodness of fit by looking at normal QQ plots for the residuals and plots of the residuals over predicted values.

The primary analysis will be performed using the Per Protocol Set.

#### SAS procedure:

```
proc mixed data = dataset method = REML plots=all;
  class Seq Per Trt subj gender;
  model  $\Delta QTcF = \text{Baseline } Seq Per Trt gender /$  ddfm = kr residual outp=ipred outpm=pred;
  random subj / type = cs;
```

CONFIDENTIAL	STATISTICAL ANALYSIS PLAN N° GDX-44-006  VERSION N° 2.0      DATED: 24JUL2018  ██████████	██████████  Page 27 / 57
--------------	---	--------------------------------

```
lsmeans Trt;
Estimate "P03277 0.1 mmol/kg - Placebo 5min after administration" Trt 1 0 0 -1 / alpha = 0.1
cl;
run;
```

### 5.5.2. Supportive analyses of primary criterion

Primary analysis will be repeated using the Full Analysis Set.

#### Assay sensitivity analysis

The assay sensitivity analysis is performed using an analysis of covariance (ANCOVA) model for crossover data with baseline data as covariate, sequence, period, trial drug and sex as fixed effect and subject as a random effect.

#### Test:

Differences between means will be tested through the model for each timepoint using Student's t-test. Only the five following timepoints will be used: 1h, 1h30, 2h, 3h and 4h.

For each timepoint, the p-value for comparing the doses of positive control with corresponding placebo is calculated for testing above hypotheses.

#### Hochberg's step-up procedure:

Let  $p_1, p_2, p_3, p_4, p_5$  be the ordered p-values (from the lower to the upper value) and  $H_1, H_2, H_3, H_4, H_5$  be the corresponding ordered null hypothesis. The testing procedure starts with the less significant comparison and continues as long as tests are not significant (meaning that the alternative hypothesis is not met). The procedure stops the first time a significant comparison occurs and all remaining hypotheses will be not tested.

- In the first step,  $H_5$  is rejected if  $p_5 \leq \alpha$ ,
- in the second step (if any)  $H_4$  is rejected if  $p_4 \leq \alpha/2$ ,
- in the third step (if any),  $H_3$  is rejected if  $p_3 \leq \alpha/3$ ,
- in the fourth step,  $H_2$  is rejected if  $p_2 \leq \alpha/4$ ,
- and in the fifth and last step,  $H_1$  is rejected if  $p_1 \leq \alpha/5$  with  $\alpha$  being the 1-sided significance level of 0.05.

The trial will be considered as positive in terms of assay sensitivity if, at the end of the Hochberg's step-up procedure, at least one test is significant. CI will be adjusted according to the procedure.

Assay sensitivity will be repeated using the Per Protocol Set.

#### SAS procedure:

```
proc mixed data = dataset method = REML plots=all;
class Seq Per Trt subj gender;
model ΔQTcF = Baseline Seq Per Trt gender / ddfm = kr residual outp=ipred outpm=pred;
random subj / type = cs;
lsmeans Trt;
Estimate "Positive control - Placebo 1hour after administration" Trt 0 0 1 -1 / alpha = 0.1 cl;
```

CONFIDENTIAL	
STATISTICAL ANALYSIS PLAN N° GDX-44-006
 
VERSION N° 2.0      DATED: 24JUL2018
	
██████████
 
Page 28 / 57

--------------	--	---

run;

### 5.5.3. Additional analyses of primary criterion

Not Applicable.

### 5.5.4. Analysis of secondary criteria

Analysis of secondary criteria will be done using the Full Analysis Set except otherwise specified.

#### 5.5.4.1 Primary endpoint

Same analysis as for primary end-point will be repeated for QT, QTcPOP, QTcB and HR.

#### 5.5.4.2 Descriptive analysis

- Descriptive statistics (number [n], mean, standard deviation [SD], median, minimum, and maximum) at any time from administration up to 24h post dose of time-matched change from baseline, placebo controlled, of the QT, QTcF, QTcPOP and the QTcB will be provided by trial product group.
- Number and percentage of subjects showing values above predefined threshold for PR, QRS, QT, QTcB, QTcPOP and QTcF:
  - PR interval
    - Value > 220 ms
    - Relative change > 25%
  - QRS interval
    - Value > 120 ms
    - Relative change > 25%
  - Absolute QTc interval prolongation:
    - QTc interval > 450 ms
    - QTc interval > 480 ms
    - QTc interval > 500 ms
  - Change from baseline in QTc interval:
    - QTc interval increases from baseline > 30 ms
    - QTc interval increases from baseline > 60 ms
- Descriptive statistics (number [n], mean, standard deviation [SD], median, minimum, and maximum) at any time of QT, QTcF, QTcPOP, QTcB, RR (ms), QRS (ms), PR (ms), Heart rate (bpm) will be presented by trial product group. Frequency and percentages will be calculated for interpretation. The worst case of interpretation by triplicates (Abnormal clinically significant > Abnormal non clinically significant > Unable to evaluate/unable to evaluate but measurements provided are correct > Normal ECG) will be presented.

CONFIDENTIAL	STATISTICAL ANALYSIS PLAN N° GDX-44-006  VERSION N° 2.0      DATED: 24JUL2018  	  Page 29 / 57
--------------	--	---

- Frequency and percentages will be calculated for sinus rhythm (yes/no) globally by trial product group. The number (%) of subjects having at least one “No” for sinus rhythm or having all “Yes” after baseline will be summarized.

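### PR and QRS get descriptives, outlier counts and safety-ECG changes, but no modelled placebo-corrected effect with a 90% confidence interval

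*SAP*

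**What the plan says.** Protocol 7.2.1 and SAP 2.2.2 list PR and QRS among the secondary cardiac safety criteria. Both come from the centrally read Holter triplicates. As for QTcF, each period has its own pre-dose baseline and each post-dose time has a matching placebo time.

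The primary model (SAP 5.5.1.2) is an "analysis of covariance (ANCOVA) model for crossover data with baseline data as covariate, sequence, period, trial drug and sex as fixed effect", with subject random and one model per timepoint. From it, "the two-sided 90% confidence intervals of the difference between each of the two doses of P03277 and placebo is calculated". SAP 5.5.4.1 then extends this model: "Same analysis as for primary end-point will be repeated for QT, QTcPOP, QTcB and HR". The placebo-controlled descriptives in SAP 5.5.4.2 have a similar scope: "time-matched change from baseline, placebo controlled, of the QT, QTcF, QTcPOP and the QTcB will be provided by trial product group". Neither list contains PR or QRS.

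The text plans four things for PR and QRS:

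- Holter descriptives (n, mean, SD, median, minimum, maximum) "at any time of QT, QTcF, QTcPOP, QTcB, RR (ms), QRS (ms), PR (ms), Heart rate (bpm) will be presented by trial product group" (SAP 5.5.4.2).
- Outlier counts: "Number and percentage of subjects showing values above predefined threshold for PR, QRS, QT, QTcB, QTcPOP and QTcF". The limits are 220 ms for PR, 120 ms for QRS, and a relative change above 25% for either. SAP section 4 records this as an addition to the protocol: "Descriptive analysis on number and percentage of subjects showing values above predefined threshold will be presented for PR and QRS".
- Core-lab safety ECGs before each dose, at 10 minutes, at 3 hours and on Day 12, tabulated as raw values and change from baseline by product (SAP 2.3.1.5 and 5.6.5).
- Counts of subjects with emergent morphological findings, including AV and intraventricular conduction (SAP 5.5.4.4).

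**The concern.** The crossover yields a within-subject comparison with placebo for every Holter interval, and the plan uses it for QT, its corrections and HR. For PR and QRS it stops at summaries by product. None of the four outputs is a placebo-corrected mean effect with an interval.

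What is at stake is how precisely the trial can describe any effect on AV conduction or ventricular depolarisation. The by-product means show a point difference, but the SDs beside them include the spread between subjects, which the design was chosen to remove. The counts respond to large individual changes and hardly at all to a modest shift shared by everyone. The safety ECGs do give change from baseline, but at few times (the first post-dose one at 10 minutes, whereas Holter starts at 5 minutes) and with no contrast against placebo.

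**Working it through.** **Plan's own figure.** The plan states no number for PR or QRS. Its only variability figure is the QTcF within-subject SD of 9 ms behind the 40 evaluable subjects (Protocol 11.2, SAP 3.3). The stated formula with L = 9 gives 37.9, so 38, or 40 when rounded up to a multiple of the four sequences. That figure is sound and does not depend on this point.

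**Inputs for the comparison.**
- From the documents: 48 randomised, and recruitment may stop once 40 are evaluable; eligible PR 120 to 200 ms and QRS up to 100 ms at screening (Protocol 4.2, criterion 8); the outlier limits above.
- Assumed: PR between-subject SD 15 to 20 ms; PR within-subject SD 6 to 9 ms, the upper end borrowed from QTcF.

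**Step 1: standard error from the tables.** A tabulated SD of raw values holds both variance components, so SE = √(2/n) × √(SD_between² + SD_within²). With n = 48, √(2/48) = 0.204.
- Low: √(15² + 6²) = 16.2, giving 3.3 ms.
- High: √(20² + 9²) = 21.9, giving 4.5 ms.

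**Step 2: standard error from the crossover model.** SE = √(2/n) × SD_within.
- Low: 0.204 × 6 = 1.2 ms.
- High: 0.204 × 9 = 1.8 ms.

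At n = 40 everything grows by √(48/40) = 1.095: about 3.6 to 4.9 ms against 1.3 to 2.0 ms.

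**Step 3: 90% half-widths.** With t(0.95, 46) ≈ 1.68 and n = 48, the half-width is about 5.5 to 7.5 ms from the tables and 2.1 to 3.1 ms from the model. Over a wider assumed within-subject SD of 3 to 9 ms, which may suit QRS better at its lower end, the model gives 1.0 to 3.1 ms at n = 48 and 1.1 to 3.4 ms at n = 40.

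**Step 4: what the counts can see.** From baseline b, PR becomes an outlier through a rise above the smaller of 220 − b and 0.25b.

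| Baseline PR (ms) | 220 − b | 0.25b | Rise needed (ms) |
|---|---|---|---|
| 120 | 100 | 30 | 30 |
| 160 | 60 | 40 | 40 |
| 176 | 44 | 44 | 44 |
| 200 | 20 | 50 | 20 |

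The least demanding eligible baseline is 200 ms, which still needs 20 ms. For QRS the rule is the smaller of 120 − b and 0.25b. Over an assumed baseline range of 80 to 100 ms that is again at least 20 ms (20 at 80, 24 at 96, 20 at 100). If dosing baselines resemble screening values, a uniform rise of 10 ms in either interval crosses a limit only where within-subject noise supplies the rest.

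**Step 5: size of the addition.** 2 parameters × 11 timepoints × 2 doses = 44 intervals. At 90% coverage with no true effect, 44 × 0.10 = 4.4 would be expected to exclude zero.

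**The case against.** The strongest reply is that the two tiers are deliberate. The protocol asks for placebo-corrected effects on QT and its corrections and lists PR and QRS simply as parameters measured over time. The primary objective concerns QT and QTc, and no margin or decision rule exists for PR or QRS. HR earned its place in the model because SAP 5.5.4.3 uses the placebo-corrected HR course when checking the concentration-response model; PR and QRS have no such role. All of this stands. It shows that the omission is neither an inconsistency with the protocol nor arbitrary, but it is no reason against a better estimate of a named safety criterion.

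Three stronger readings are tempting, and the documents support none of them:

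- That PR and QRS are summarised only as raw Holter values. The outlier counts (with a change-based rule), the safety-ECG changes from baseline and the morphology counts all go further.
- That the trial could not state the size of an effect. Product mean minus placebo mean at the same time is a point estimate, unbiased in a balanced crossover with complete data, and both means are tabulated.
- That no interval could be derived. The tabulated SDs give one. It is merely too wide when a subject's values are positively correlated across periods. Individual data are also listed, so the contrast could be computed later, though not as a pre-specified result.

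The reply is also right that the SDs used here are assumptions. Finally, the contents of SAP section 6 (the output list) are not visible in the public version, so an extra table there cannot be excluded; the SAP text describes none.

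**Conclusion.** The point holds as a modest gap. PR and QRS are secondary cardiac safety criteria for which the text plans no modelled, placebo-corrected change from baseline and no 90% interval, although the design supports both.

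Under the assumed PR SDs, the crude comparison has a standard error roughly 2.4 to 2.7 times that of the model (4.5/1.8 = 2.5 and 3.3/1.2 = 2.7 from the rounded values; 21.9/9 = 2.4 and 16.2/6 = 2.7 from the SDs). The practical loss falls on shifts of a few milliseconds, which the model could separate from zero and the tables could not. A uniform shift of about 10 ms would show in the by-product means but go largely unseen by the outlier counts. The threshold arithmetic rests on the documents for PR and on an assumed baseline range for QRS; the ratio of standard errors rests wholly on assumed SDs.

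A reader might infer that the QT conclusion is weakened. It is not: the QTcF analysis, assay sensitivity and sample size are untouched. This is a worthwhile improvement rather than a defect that threatens the trial.

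**What to change.** In SAP 5.5.4.1, add PR and QRS to the parameters for which the per-timepoint model is repeated (baseline, sequence, period, product and sex, with random subject). Report the placebo-corrected change from baseline with a two-sided 90% interval for both doses. State that this is estimation only, that the 10 ms margin does not apply, and that the intervals are descriptive and unadjusted. Keep the threshold counts, which answer a different question about individuals.

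The cost is one SAP sentence, two further runs of existing code and a few tables. Sample size and the Type I error of the confirmatory tests do not change. The real drawback is interpretive: of the 44 added intervals, about 4 would exclude zero by chance, which is why the descriptive label matters.
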